6.2 Handling/storage/responsibilities

6.2.1 Dosage form, appearance, packaging and labeling

See 6.1.1

6.2.2 Product storage and stability

See 6.1.1

6.3 Adherence to study intervention

The study treatment will be administered in the hospital under the supervision of the investigator, so compliance can be easily monitored. The date of intravenous infusion and the exact amount of each infusion will be recorded on the CRF.

For all study drugs, if the administration is interrupted during the infusion, the clinical medical staff should assess the percentage of the drug received by the subject and record it in the CRF.

The reason for any noncompliance should also be recorded. Inadequate compliance is defined as a subject missing more than 2 doses or follow-up visits for non-medical

reasons. In the case of inadequate compliance, the investigator and co-investigator will consider discontinuing the administration of the study drug based on the individual circumstances of the subject.

6.4 Combination therapy

For this study, prescription drugs were defined as drugs that can only be prescribed by authorized/qualified clinicians. Medications recorded in the case report form (CRF) refer to concomitant prescription drugs, over-the-counter drugs, and supplements.

7. Discontinuation of study intervention and subject discontinuation/withdrawal

7.1 Study intervention discontinuation

Suspension of study intervention does not mean suspension of the study, and subsequent study procedures should be completed in accordance with the provisions of the trial protocol. If clinically significant changes occur after enrollment (including but not limited to changes from baseline levels), the investigator will decide whether the subject management needs to be changed. Any new clinically relevant findings will be reported as adverse events (AEs).

7.1.1 Criteria for discontinuation of study intervention

In the event of any of the following circumstances, the subject must discontinue the study intervention

- 1)If a clinically relevant event occurs that seriously affects the safety of the subject, the investigator or sponsor considers it necessary to terminate the intervention;
- 2)Imaging examinations to determine disease progression;
- 3)The subjects received other study drugs or chemotherapy during the clinical study;
- 4)Lack of compliance by subjects;

- 5)The subject becomes pregnant during treatment;
- 6)Elective surgery.

7.1.2 Data collected at the time of discontinuation of the study intervention

Patients who withdraw from the study early should complete all necessary examinations and steps of the study to ensure the integrity of the study. All reasons and dates for stopping the study should be recorded in the CRF.

7.1.3 Subject discontinuation/withdrawal from study

- 1)Patients may request to withdraw from the study at any time.
- 2)Researchers may ask subjects to terminate or withdraw from the study for the following reasons:
 - Pregnancy;
 - Poor compliance with study interventions;
 - If a clinical adverse event (AE), laboratory abnormality, or other medical condition occurs, continued participation in the study will not be in the best interest of the subject;
 - Disease progression requiring discontinuation of intervention;
 - The subject meets the exclusion criteria (new or previously undetected) and cannot continue to participate in the study;
 - Subjects are unable to receive regularly scheduled study interventions.
- 3)A subject to discontinue or withdraw from the study should be recorded in the case report form (CRF). Subjects who signed informed consent and underwent randomization but did not receive the study intervention can be replaced. Subjects who signed informed consent, underwent randomization, received the study intervention, and subsequently withdrew or were withdrawn/discontinued from the study cannot be replaced.

7.2 Lost to follow-up

If a subject does not return to the study center for two consecutive scheduled visits and the study center staff cannot contact him/her, he/she will be considered lost to follow-up.

If a patient does not return to the study center for a scheduled study visit, the following actions must be taken:

- The research center attempts to contact the subject (for up to 2 visit cycle time points) to explain to the subject the importance of adhering to the visit schedule and to confirm whether the subject is willing and/or should continue to participate in the study;
- Before a subject is considered lost to follow-up, the investigator or designee will make every effort to re-contact the subject (by making three phone calls if possible and, if necessary, by sending a registered letter to the subject's most recent mailing address or locally available contact information). These attempts to contact the subject should be recorded in the subject's medical record or study files;
- If the subject still could not be contacted, he/she was considered lost to follow-up and dropped out of the study.

8. Research evaluation t and process

8.1 Efficacy evaluation

The starting point of efficacy evaluation is the time when the subject first receives treatment

8.1.1 Disease progression as the endpoint

- 1)The event endpoint was the time to disease progression in the subject;
- 2)If disease progression is confirmed but the time of disease progression

cannot be determined, the last imaging examination time of the subject without disease progression is used as the event endpoint;

3)For patients who died of any other cause before disease progression, the time of death of the subject will be used as the event endpoint;

4)For subjects who have not experienced disease progression or death (i.e., progression-free survival) at the time of analysis, the time of the last tumor assessment will be used as the event endpoint;

5)For subjects lost to follow-up, the time to the last tumor assessment without disease progression will be used as the event endpoint;

6)For subjects who only have baseline imaging examination, the time of baseline examination will be used as the event endpoint.

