4.1.1 Screening period

●Definition: within 3 weeks before drug administration

●Content:

- 1) Sign the informed consent form;
- 2) Screening;
- 3) Demographic characteristics;
- 4) History of present disease;
- 5) Past medical history;
- 6) Combined treatment;
- 7) Body surface area (BSA);
- 8) Physical examination
- 9) Vital signs;
- 10) ECOG performance status: see 12.1. ECOG performance status scoring standards;
- 11) Nutritional status: see 12.4. Nutritional risk screening form (NRS 2002);
- 12) Quality of life: see 12.5. Quality of life score (QoL) of cancer patients;
- 13) Charlson Comorbidity Index: see 12.6. Charlson Comorbidity Index scoring criteria and calculation method;
- 14) Initial tumor imaging assessment:
 - a.Oral and intravenous contrast-enhanced CT (neck + chest + abdomen, and pelvis if necessary) is preferred;
 - b.Optional items include intraesophageal ultrasound, bone scan, esophageal fiber endoscopy, esophageal barium meal, PET/CT, etc.
- 15) Electrocardiogram (12 leads);
- 16) Laboratory examination of blood samples (hematology and

biochemistry);

17) Pregnancy test (female subjects of childbearing age);

18) Adverse events were observed and recorded.

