8.1.2 Events ending in death

1)The event endpoint was the time of subject death;

2)If the subject's death is confirmed but the time of death is not clear, the last follow-up time of the subject is taken as the event endpoint;

3)For patients who had not died at the time of analysis, the time of the last follow-up was used as the event endpoint;

4)For patients lost to follow-up, the time of the last follow-up was used as the event endpoint;

5)For patients with only survival, the time of baseline examination will be used as the end point.

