9.2 Analysis population

- 1) Full analysis set (FAS): All patients diagnosed with distant metastasis or recurrence of esophageal cancer who received trial drug treatment and had at least one post-drug efficacy follow-up data were included in the full analysis set.
- 2) Per-protocol set (PPS): Subjects who met the main inclusion and exclusion criteria, completed the trial drug treatment and follow-up observation according to the protocol, and had complete survival data were included in the per-protocol set.
- 3) Safety analysis set (SS): All subjects who received trial drug treatment and for whom at least one post-dose safety data was available were included in the safety analysis set.

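### PFS item 6 and OS item 5 date subjects at the baseline examination, at or before time zero, and overlap with the death and last-follow-up rules without any order of precedence

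*Protocol*

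**What the plan says.** Section 8.1 of the protocol sets time zero: "The starting point of efficacy evaluation is the time when the subject first receives treatment". The screening period in section 4.1.1, in which baseline is assessed, is placed earlier: "Definition: within 3 weeks before drug administration".

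Section 8.1.1 then lists six dating rules for PFS. Two matter here:

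- Item 3: "For patients who died of any other cause before disease progression, the time of death of the subject will be used as the event endpoint".
- Item 6: "For subjects who only have baseline imaging examination, the time of baseline examination will be used as the event endpoint".

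Items 4 and 5 date subjects without an event, and those lost to follow-up, at the last tumor assessment.

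Section 8.1.2 does the same for OS:

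- Item 1: "The event endpoint was the time of subject death".
- Item 3: "For patients who had not died at the time of analysis, the time of the last follow-up was used as the event endpoint". Item 4 applies the same date to subjects lost to follow-up.
- Item 5: "For patients with only survival, the time of baseline examination will be used as the end point".

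Neither list ranks its items. Both use the same term for every date, whether the subject had an event or is to be censored.

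Section 9.2 limits the full analysis set to treated subjects who "had at least one post-drug efficacy follow-up data were included in the full analysis set".

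**The concern.** Three things do not fit together.

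- Subjects dated at the baseline examination get a survival time of zero or less.
- A subject who dies before the first post-baseline scan has baseline imaging only. PFS items 3 and 6 both apply and give different dates. Item 6 adds almost nothing for living subjects, because for someone with baseline imaging only, the last tumor assessment in items 4 and 5 already is the baseline examination. The group whose result item 6 can change is mainly those who died.
- OS item 5 sends some subjects back to baseline although items 3 and 4 would date the same subjects at last follow-up. Section 4.1.5 allows survival status to be collected by telephone, so having survival information and nothing else is a foreseeable situation.

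At stake is whether a few early deaths count in the primary endpoint of a single-arm trial, where no control arm would offset an upward shift, and whether known survival time is kept in OS.

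**Working it through.** The plan gives no figure for this point, so the check is a comparison of the rules followed by a sizing under stated assumptions.

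**Inputs**

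- Time zero: first treatment (section 8.1).
- Baseline: up to 21 days earlier (section 4.1.1).
- First post-baseline scan: day 22, imaging window ±7 days, so day 15 to 29 (section 4.1.2).
- Median PFS: 16 months reference, 18.2 months expected, gain 18.2 − 16 = 2.2 months (section 9.1).
- N = 52 (section 9.1): 41/(1 − 0.20) = 51.25, rounded up. Whether 41 itself follows from the stated medians is a separate matter and does not enter here.
- Assumptions: exponential PFS; 30.4375 days per month.

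**Step 1: the negative times.** A subject dated at baseline has a time between −21 and 0 days. If that is a censoring time, the subject is in no risk set at any later event. Dropping the record or censoring it at day 0 gives the same Kaplan-Meier curve. This part of the defect has no numerical effect.

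**Step 2: the overlap.** For a subject with baseline imaging only:

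- Alive: items 4, 5 and 6 all give the baseline date. They agree with each other, but the date is at or before time zero.
- Dead before the first scan: item 3 gives the date of death and item 6 the baseline date. No order is stated.

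**Step 3: how many subjects could be affected.** P(event before day d) = 1 − exp(−ln 2 × d / (30.4375 × median)).

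| Scan day | Median 16 months | of 52 | Median 18.2 months | of 52 |
|---|---|---|---|---|
| 15 | 2.1% | 1.1 | 1.9% | 1.0 |
| 22 | 3.1% | 1.6 | 2.7% | 1.4 |
| 29 | 4.0% | 2.1 | 3.6% | 1.9 |

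This counts all PFS events, so it is an upper guide for deaths: about one or two of 52.

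**Step 4: effect if item 6 is applied to those deaths as censoring.** Removing k early deaths multiplies the later curve by 52/(52 − k). For an exponential curve the median then rises by ln(52/(52 − k)) × 16/ln 2, where 16/ln 2 = 23.08.

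- k = 1: ln(52/51) × 23.08 = 0.0194 × 23.08 = 0.45 month (20% of 2.2).
- k = 2: ln(52/50) × 23.08 = 0.0392 × 23.08 = 0.91 month (41% of 2.2).

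With the 50 subjects given in the section 1.1 summary the figures are nearly the same: ln(50/49) × 23.08 = 0.47 and ln(50/48) × 23.08 = 0.94 month.

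A simulation (3,000 runs per k, 24 months of follow-up) confirms the multiplier. Twelve-month PFS was 0.600 with one early death counted and 0.612 with it dropped (ratio 1.02 = 52/51). With two deaths it was 0.590 and 0.614 (ratio 1.04 = 52/50). Simulated sample medians move in coarse steps at this size (0.87 month for both k = 1 and k = 2), so the formula is used for the median.

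**Step 5: OS.** Deaths are safe under item 1. For a living subject whose only post-baseline information is survival status, items 3 and 4 give the last contact and item 5, read literally, gives baseline. All known survival time for that subject would be lost.

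**The case against.** The strongest reply is that items 1 to 3 deal with events and items 4 to 6 with subjects who had none, so item 3 naturally governs any death and item 6 only completes items 4 and 5. That is a sensible reading, and under it there is no bias. It is not written down, however. Item 3 also speaks of death from another cause, which leaves some doubt about a death from the esophageal cancer itself before any scan.

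A reader might infer that the plan drops early deaths and so biases PFS upward. The text does not settle that. Deaths are lost only if item 6 prevails and is treated as censoring. Read literally as an event date, item 6 would turn living baseline-only subjects into failures at or before time zero, which lowers PFS.

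A reader might also posit a larger effect, say 8% early deaths (4 of 50), which would move a 16-month median to 17.9 months. Under the same exponential model 8% is reached only at 0.0834 × 23.08 = 1.92 months, about day 59. By then the day-22 scan and the scan within one week after radiotherapy (section 1.3, note 2) are both due. Entry also requires ECOG 0–1 and an expected survival of at least 12 weeks. The documents do not support that case.

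The full analysis set condition may already exclude subjects with baseline data only, so item 6 might apply to nobody analysed. This stands as a limit on the claim, but it does not clear the rule. If death counts as efficacy data, the conflict between items 3 and 6 is live. If it does not, the same early deaths are lost through section 9.2.

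Finally, OS item 5 may be meant for subjects with baseline data only, by analogy with PFS item 6. Then no known survival time is discarded, but the wording still needs correcting and the date is still at or before time zero.

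**Conclusion.** The point holds as a defect in stated dating rules. PFS item 6 and OS item 5 give times at or before time zero. PFS items 3 and 6 conflict for deaths before the first scan, and OS item 5 as worded conflicts with OS items 3 and 4. The negative times by themselves change nothing in the Kaplan-Meier estimate.

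The possible effect on the primary endpoint is conditional. If item 6 were applied as censoring to one or two early deaths among 52, median PFS would read about 0.45 to 0.9 month too high, against a planned gain of 2.2 months. If item 3 prevails, or no such deaths occur, the effect is nil. The size rests on an exponential curve with a 16-month median, on these subjects being in the full analysis set, and on using all early PFS events as the guide for deaths, since the protocol gives no early-death rate. It is worth correcting before analysis; it does not show that the planned PFS estimate is biased.

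**What to change.** Four short changes to the text:

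- **PFS, section 8.1.1:** state that any documented death without prior progression, from any cause, is an event on the date of death and overrides item 6.
- **PFS, item 6:** state that a living subject with no post-baseline tumor assessment is censored on the day of first treatment.
- **OS, section 8.1.2, item 5:** replace with censoring at the last date known alive from any source, including telephone contact, or on the day of first treatment if there is none.
- **Section 9.2:** state that death or survival status satisfies the full analysis set condition of post-drug efficacy data. Without this, the first change would not bring back an early death that section 9.2 had already excluded.

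The cost is a few sentences. No visit, data item or sample size changes, because date of death, survival contacts and first treatment are already collected.

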8.1.2 Events ending in death

1)The event endpoint was the time of subject death;

2)If the subject's death is confirmed but the time of death is not clear, the last follow-up time of the subject is taken as the event endpoint;

3)For patients who had not died at the time of analysis, the time of the last follow-up was used as the event endpoint;

4)For patients lost to follow-up, the time of the last follow-up was used as the event endpoint;

5)For patients with only survival, the time of baseline examination will be used as the end point.

8.2 Adverse events and serious adverse events

8.2.1 Definition of adverse events (AEs)

Adverse events refer to unexpected medical events related to or unrelated to the use of a drug. In this study, adverse events were judged from the subject screening period regardless of whether they were causally related to the trial drug.

8.2.1.1 Examples of adverse events include:

- 1)A worsening of a chronic disease or the continued presence of symptoms, including an increase in the frequency and/or intensity of symptoms;
- 2)New symptoms detected or diagnosed after administration of the investigational drug, even if the symptom may have existed before the start of the study;
- 3)Doubt caused by the interaction between the signs, symptoms or clinical sequelae;
- 4)Signs, symptoms, or clinical sequelae of overdose of the investigational drug or concomitant medication (overdose, by its nature, should not be reported as an AE/SAE);

When a patient dies, the cause of death is the AE, and death is the outcome of the adverse event.

8.2.1.2 Examples of adverse events do not include:

- 1)Medical or surgical procedures (endoscopy, appendectomy); the circumstances leading up to these procedures are AEs, not the surgical procedures themselves;
- 2)Situations in which adverse medical events did not occur (socially and/or recognizable to the hospital);
- 3)Pre-existing disease with early day-to-day fluctuations or no worsening of symptoms present or detected at study entry;
- 4)The disease/condition being studied, or the expected progression, signs, or symptoms of the disease/condition being studied, unless more severe than expected for the subject;
- 5)In principle, "lack of efficacy" or "failure to achieve the expected pharmacological effect" is not reported as an AE or SAE. However, signs, symptoms and/or clinical sequelae caused by lack of efficacy will also be reported as AEs or SAEs if they meet the definition of AEs or SAEs.

8.2.2 Definition of serious adverse event (SAE)

If the researchers or bidders think adverse events (AE) or suspected adverse reactions can lead to the following consequences, should be considered a serious: death, life-threatening adverse events, prolonged hospitalization, or hospital, affect the normal life of persistent or significant disability/disability, congenital abnormalities and/or birth defects.

Based on appropriate medical judgment, major medical events that are unlikely to result in death, be life-threatening, or require hospitalization may be considered serious adverse events when the event is likely to endanger the subject and may require medical or surgical intervention to prevent one of the outcomes listed in the above definition. Examples include allergic bronchospasm requiring intensive treatment in the emergency room or at home, cachexia or seizures that do not result in hospitalization, and the development of drug dependence or drug abuse.

Death (defined as Grade 5 by NCI-CTCAE Version 5.0) is generally considered the outcome of the event. If death occurs, the primary cause of death (the main cause of death) will be recorded as the SAE. "Fatal" will be recorded as the outcome of this adverse event; death should not be recorded as a separate event. Death itself will only be recorded as an SAE when the cause of death cannot be determined (e.g., sudden death, unexplained death).

8.2.3 Adverse event classification

8.2.3.1 Severity of the incident

Investigators will refer to the National Cancer Center Common Terminology Criteria for Adverse Events (NCI-CTCAE) version 5.0 to evaluate adverse events. This standard uses descriptive terms when reporting AEs. Investigators are required to grade the severity of each adverse event. If the severity/intensity of an adverse event is not clarified in the guidelines, the investigator may make an assessment based on the general definition of 1-5 and combined with his or her best medical judgment.

The general classification is:

Grade 1: Mild;

Grade 2: Moderate;

Grade 3: Severe;

Grade 4: Life-threatening or disabling;

Grade 5: AE-related death.

8.2.3.2 Relevance to the study intervention

The clinician examining and evaluating the subjects must assess the relevance of all adverse events to the study intervention based on the timing and his/her clinical judgment. In clinical studies, the study intervention must always be a subject of suspicion.

Grading of relevance of study intervention:

- 1) Definitely related: There is clear evidence of a causal relationship and other possible factors can be ruled out. The clinical event (including abnormal laboratory test results) occurs in a reasonable time relationship with the administration of the study intervention and cannot be explained by concurrent illness, other drugs or chemicals. The response of withdrawing the study intervention (de-challenge) should be clinically reasonable. The event must be pharmacologically or phenomenologically clear, and if necessary, a qualified re-challenge procedure can be used;
- 2) Probably related: There is evidence of a causal relationship and the likelihood of other factors being influential is low. The clinical event (including laboratory abnormalities) occurred within a reasonable period of time after the study intervention was given and is unlikely to be attributed to concurrent illness, other drugs or chemicals, and is consistent with a clinically reasonable withdrawal (de-challenge) response. No re-challenge information is required to complete this definition;
- 3) Possibly related: There is some evidence of a causal relationship (e.g., the

event occurred within a reasonable period after administration of the trial drug). However, other factors may have contributed to the event (e.g., the subject's clinical condition, other concomitant events). Although an adverse event may be classified as "possibly related" soon after discovery, it can be recorded as requiring more information and then upgraded to "probably related" or "definitely related" depending on the circumstances;

- 4) Likely unrelated: The temporal relationship between the clinical event (including laboratory abnormalities) and the administration of the study intervention indicates that a causal relationship is unlikely (e.g., the event did not occur within a reasonable period after the administration of the study intervention), and other drugs, chemicals, or underlying diseases can provide a reasonable explanation (the subject's clinical condition, other concomitant treatments);
- 5) Definitely Unrelated: The adverse event is completely independent of the study intervention and/or there is evidence that the event is definitely related to another etiology. There must be a clear etiology documented by the clinician.

